Sponsor	The sponsor is the party that commissions the organisation or performance of the research, for example a pharmaceutical company, academic hospital, scientific organisation or investigator. A party that provides funding for a study but does not commission it is not regarded as the sponsor, but referred to as a subsidising party.
TEI	Transforaminal Epidural Injection
TEIAS	Transforaminal Epidural Injection in Acute Sciatica
VAS	Visual Analogue Scale
WMO	Medical Research Involving Human Subjects Act; in Dutch: Wet Medisch-wetenschappelijk Onderzoek met Mensen

SUMMARY

Rationale: To study (cost) effectiveness of the transforaminal epidural injection with analgesic and anti-inflammatory medication (TEI) in order to relieve the symptoms and to evaluate the intervention as a predictor tool for symptoms of sciatica in the long term.

Objective: To evaluate the percentage of patients that experience satisfactory (long term) decrease in leg pain in the TEI group in comparison to the conservative care group.

Study design: Randomised controlled trial

Study population: Patients that suffer 3-8 weeks from sciatica (Numeric Rating Scale ≥ 6 , on a 10 point scale)

Intervention: transforaminal epidural injection with analgesic and anti-inflammatory medication

Main study parameters/endpoints: the percentage of patients that experience satisfactory decrease (NRS lower than 4) in leg pain after 2, 10 and 21 weeks after randomization in both treatment arms

Nature and extent of the burden and risks associated with participation, benefit and group relatedness: the participants fill in questionnaires at baseline, at 1, 2, 4, 10 and 21 weeks after randomization. Participants will also fill in cost-diaries during this period. TEI as an intervention tool is considered usual care for sciatica patients, though the timing of the injection is not clearly defined. The extent of risk from TEI is comparable to usual care.

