1. INTRODUCTION AND RATIONALE

Sciatica is a condition of radicular pain in the leg and is usually caused by herniation of a lumbar intervertebral disc. The herniated disc compresses a lumbar nerve root that continues its route into the sciatic nerve. About 13% to 40% of all people will suffer from sciatica at least once during their lifetime [1]. Sciatica can have severe socio-economic effects; patients are immobilised by the pain they experience and therefore cannot go to work or participate in social events.

Most cases resolve spontaneously with conservative therapy using only standard analgesics and/or physiotherapy. In a large RCT it was demonstrated that outcome of conservative and surgical therapy was comparable after 26 weeks [2]. 40% of patients randomized to the conservative care group crossed over and was treated surgically, with a mean delay of 15 weeks. With this knowledge the guidelines for surgical treatment of sciatica were adjusted and it is nowadays usual care to offer surgery only after at least 8 weeks of conservative care and preferably after 14-16 weeks of conservative care. This decision is made together with the patient in a process of Shared Decision making [3,4].

Although this treatment regimen has been demonstrated to be efficacious and cost effective, the burden for a patient during these weeks of conservative care is usually high. We seek to find a type of conservative care to reduce the discomfort due to the pain and to enable the patient to remain physically active. Not only will this add to the quality of life of the patient, but it will also prevent the patient from taking a sick-leave.

Rationale for this study

We would like to explore the effectivity of the transforaminal epidural injection (TEI) with analgesic and anti-inflammatory medication to relieve the symptoms. Theoretically, such an injection would have a painkilling effect within the first two weeks after injection, and this effect may last for months, but we know that some patients do not experience this beneficial effect [5]. Some patients report initial pain reduction but report a re-arousal of pain after several hours, days or weeks [6].

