Costs (Cost intervention, health care use, and loss of productivity): Cost diaries will be filled out at 10 and 21 weeks after randomisation. Health care utilization (including physiotherapy, visits to GP and specialists, nursing care and medication), patient costs, and absenteeism will be measured using cost diaries filled out by the patient.

Complications: Post-TEI exacerbation of NRS leg pain (>1 point additional leg pain) that lasts for at least 24 hours will be documented as a clinically relevant complication of TEI. Other rare adverse events from treatment with TEI such as pain at site of injection, persisting numbness, vasovagal reaction, accidental discal puncture, accidental dural puncture or headache will be recorded as well.

Radiological parameters: the level of disc herniation, the size and shape of disc herniation, disc degeneration (Pfirrmann scale), vertebral end plate changes, and facet degeneration (Weishaupt scale) will be evaluated by two independent researchers, blinded to clinical and histological data, on T2 weighted sagittal and transversal MRI.

Histology: During surgery, the herniated disc material will be collected and fixed in 4% formaldehyde solution. For evaluation, the tissue will be subsequently embedded in paraffin blocks. These blocks will be stained with Hematoxylin and used for general macrophage staining (CD68), and subtype macrophage staining: M1(iNOS & CD40) and M2 (Arg1 & CD163), T cell staining (CD45-RO) and B cell staining (CD20). Furthermore, presence of Propionibacterium Acnes and Staphylococcus Epidermidis will be verified by PCR analysis for 16S rDNA. Positive samples will be gram stained for further identification of the bacteria.

All histological data will be quantified by two independent researchers, blinded to clinical and MRI data, and an inter-agreement analysis will be conducted.

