6.1.3 Other study parameters

Data with respect to the following variables will be collected at baseline:

- Demographic data;
- Age, gender, length, weight, BMI, tobacco exposure, alcohol abuse;
- History of previous radicular symptoms in the legs;
- Usage of pain medication.

Data with respect to the following items will be collected concerning TEI:

- Timing of administration (days after randomization);
- Number of injections and timing of those;
- NRS leg pain after injection;
- Other complications.

Data during follow up will be collected:

- If an MRI is performed: MRI data;
- If surgery is performed: disc material for histology.

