8.2 Secondary study parameter(s)

The absolute decline in NRS leg pain, NRS back pain and ODI and increase in EQ5D from baseline to 2 weeks after randomization will be calculated using t-tests. The same will be done for the baseline to 4 weeks after randomization time point (using t-tests).

Perceived recovery Likert data will be dichotomized (1 and 2 is success, 3-7 is no success) and compared at 2 and 4 weeks after randomization or injection and to 14 and 26 weeks after start of severe leg pain using Chi-square tests.

The 2-week success data will be correlated to the success data after 14 weeks and subsequently for 26 weeks using Chi-square tests to make predictions. Logistic regression analysis will be used to correlate 2-week (and 4-week) success data to the absolute data for NRS leg pain, NRS back pain, ODI, increase in EQ5D at 14 and 26 weeks.

Cost effectiveness analysis:

The economic evaluation will consist of a cost-effectiveness analysis from a healthcare perspective (CEA: costs per extra patient with symptom relieve, i.e. the primary outcome measure) and a cost-utility analysis from a societal perspective (CUA: costs per QALY). Both analyses will be trial-based, using patient reports, with a half-year time horizon. Healthcare use will be valued according to the Dutch guidelines. QALYs will be calculated as the area under the utility curve, estimated using the Dutch tariff for the EQ-5D. As sensitivity analysis, QALYs will also be calculated using the VAS for quality of life (with power transformation). Average costs and patient outcome will be compared according to intention-to-treat, using net-benefit analysis, and using multiple imputation to account for missing data.

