10. ADMINISTRATIVE ASPECTS, MONITORING AND PUBLICATION

10.1 Handling and storage of data and documents

Data will be collected using Castor EDC (web based secured system provided by LUMC). Baseline data will be collected during inclusion of the participant and directly registered in Castor by a researcher from the LUMC. Data on TEI, MRI and lumbar surgery will be collected from the electronic patient system Epic in Spaarne Gasthuis by the treating physician and by a researcher from the LUMC and processed in Castor. Specific data on the TEI procedure will be filled in on a paper CRF by the anaesthesiologist and subsequently processed by a researcher from the LUMC in Castor. Other data will be collected at predefined follow-up moments through digital questionnaires that the participants will fill in at home. These will be processed automatically in Castor. Castor EDC will code the patient data into untraceable ID's. All data will be safeguarded and stored for 15 years after the study is finished. All data will be handled according to the guidelines of GRP. This obligates all researchers to comply to the quality assurance standards, which include monitoring, risk assessment, privacy of patient data, and transparency of information to the patient. The LUMC will be responsible for the processing of data.

In order to warrant privacy patient data and disc material will be coded. Only with the key data can be traced back to a specific individual. The key is securely saved at the local research site and only the principal investigator, research monitor and Healthcare and Youth Inspection (Inspectie Gezondheidszorg en Jeugd) will have access to the key. No traceable data will be published. Patients will give permission for these authorities to access the key and their personal data through the informed consent. At any moment patients can withdraw their permission. Data collected before withdrawal of consent will be used. If disc material has been collected, it will be destroyed after withdrawal of consent. Analyses of disc material performed before withdrawal of consent will be used.

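### Surgery and MRI enter the cost analysis by patient report at best, although hospital records of them are already collected and are not assigned to costing

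*Combined protocol and SAP*

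**What the plan says.** Section 8.2 plans a cost-effectiveness analysis from a healthcare perspective and a cost-utility analysis from a societal one. For the data source it says: "Both analyses will be trial-based, using patient reports, with a half-year time horizon". Healthcare use is to be valued by the Dutch guidelines, and missing data are to be multiply imputed. No unit costs are given.

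Section 6.1.2 describes the instrument: "Health care utilization (including physiotherapy, visits to GP and specialists, nursing care and medication), patient costs, and absenteeism will be measured using cost diaries". On timing it adds: "Cost diaries will be filled out at 10 and 21 weeks after randomisation". The Summary is looser: "Participants will also fill in cost-diaries during this period". The heading of the cost paragraph lists the cost of the intervention as a component separate from healthcare use, but gives no source for it.

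Other sections collect some of the same events independently of the patient. Section 6.1.3 records, for the injections, "Number of injections and timing of those". Section 10.1 says: "Data on TEI, MRI and lumbar surgery will be collected from the electronic patient system Epic in Spaarne Gasthuis", to be processed in Castor, where the questionnaires are also held. No section says that these records feed the cost analysis.

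**The concern.** Cost-effectiveness is a stated objective (section 2). Surgery is the event through which the arms could plausibly differ in later cost. Section 2 expects some patients to be operated on and a substantial share to have an MRI. Section 3 makes surgery available on request to patients whose pain persists two weeks after the injection. TEI might therefore avert operations or bring them forward.

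If operations are captured incompletely, the injection is charged while part of the surgery it averts or advances is not, and the incremental cost is wrong. A diary is a weaker source for such events than the hospital record, and that record is already in the trial database. Missing diaries add a second problem: imputation would replace something the trial knows.

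**Working it through.** **The plan's own figure.** The documents state no expected cost, unit cost or surgery rate for this trial, so there is no cost figure to reproduce. The sample size in section 4.4 (128/0.9 = 142.2, stated as 142) is used below only as a number of patients.

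**Source by cost item.**

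| Item | Patient diary (6.1.2) | Trial or hospital record | Assigned to costing in 8.2? |
|---|---|---|---|
| First and repeat TEI | Injections not named; intervention cost is a separate component | Yes (6.1.3, 10.1) | Source not stated |
| MRI | Not named | Yes (10.1) | No |
| Lumbar surgery | Not named | Yes (10.1) | No |
| Hospital admission, length of stay | Not named | Not listed in 10.1 | No |
| Physiotherapy, consultations, nursing, drugs, absence from work | Named | None | Yes, by patient report |
| Care at another hospital | Only if the patient reports it | Outside the Epic system of Spaarne Gasthuis | By patient report |

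**Timing.** Section 2 places 14–16 weeks after onset, the point to which section 3 encourages postponing surgery, at about 10 weeks after randomisation. That is inside the 21-week follow-up. If the diaries are completed retrospectively, the two recall periods are 10 weeks and 21 − 10 = 11 weeks. If they are kept continuously, as the Summary allows, recall matters less.

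**Error in incremental cost.** Let U be the unit cost of an operation, p_C and p_T the proportions operated on in the control and TEI arms, and c the share of operations captured by the diaries, taken as equal in both arms.

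- True surgery contribution to incremental cost (TEI minus control): U × (p_T − p_C).
- Recorded contribution: c × U × (p_T − p_C).
- Recorded minus true: U × (p_C − p_T) × (1 − c).

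If controls have more surgery, the incremental cost of TEI is overstated. If the TEI arm has more, it is understated. The error is zero if p_C = p_T or c = 1. With unequal capture it becomes U × [p_C(1 − c_C) − p_T(1 − c_T)], and equal surgery rates no longer guarantee zero.

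**Size, in units of one operation's cost per patient** (differences and capture rates are assumptions):

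| Difference in surgery proportion | c = 0 | c = 0.5 | c = 0.8 | c = 1 |
|---|---|---|---|---|
| 0.10 | 0.10 | 0.05 | 0.02 | 0 |
| 0.20 | 0.20 | 0.10 | 0.04 | 0 |

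In euros, purely for illustration, take U between 3,000 and 8,000 (an assumption with no basis in the documents). A 10-point difference gives 300–800 per patient at c = 0 and 60–160 at c = 0.8. A 20-point difference gives 600–1,600 and 120–320.

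**Number of events.** If 10% to 40% of 142 patients were operated on by week 21, there would be 142 × 0.10 = 14.2 to 142 × 0.40 = 56.8 operations. The range is assumed. Its upper end is borrowed from the earlier trial in section 1, where "40% of patients randomized to the conservative care group crossed over and was treated surgically, with a mean delay of 15 weeks".

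**Missing diaries.** Section 4.4 allows for 142 − 128 = 14 patients lost to follow-up. If one of them had been operated on at Spaarne Gasthuis, the operation could be on file. Yet a cost variable built from patient reports would be missing for the uncovered period and would be imputed. The plan does not say that the imputation would use the recorded operation.

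**The case against.** The strongest reply is that nothing is shown to be left out. The diary list opens with a word that introduces examples, the form itself is not in the documents, and both economic perspectives point to counting surgery. Section 8.2 does not forbid other sources, and its reference to patient reports can also be read as covering the patient-reported effects. An operation is a salient event that patients are likely to report, and the documents give no evidence that they would not. Capture could be close to complete, in which case the error is close to zero. Injections are recorded separately and can be costed as the intervention.

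Most of this stands, and it limits the point. A reader might infer that the diaries exclude surgery, so that it is missed altogether. An open list does not support that: omission is a risk, not a finding. A reader might also infer that every cost, including TEI, comes from patient report. The separate intervention component, with no stated source, does not support that either.

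What the reply does not remove is that patient report is the only source the plan names for healthcare use, while a better source for injections, MRI and surgery is already collected and left unassigned. Good recall would not help a patient who returns no diary.

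**Conclusion.** The point holds as a choice of data source that should be improved, in a secondary analysis. The primary endpoint and the sample size are unaffected.

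The size is U × (difference in surgery proportion) × (1 − c) per patient when capture is equal in both arms, and it can favour either arm or be zero. None of U, the surgery proportions or c is given in the documents, so the euro amounts are illustrations only. The 40% belongs to the conservative arm of a different trial, over a period that section 1 does not state. It is not a forecast for GP-recruited patients followed for 21 weeks, most of whom may recover without surgery.

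It is tempting to conclude that the largest cost in the trial is at stake. The documents do not establish this: without unit costs or a surgery rate, absence from work could weigh more in the societal analysis.

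**What to change.** In section 8.2, state the source of each cost item:

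- All TEI procedures (first and repeat), MRI scans and lumbar operations are counted from the Epic/Castor records of sections 6.1.3 and 10.1 and valued by the Dutch guidelines.
- Diaries supply the remaining items and any care received outside Spaarne Gasthuis.
- When both sources report the same event, the hospital record takes precedence and the event is counted once.
- Costs of events on record are not imputed when a diary is missing; imputation is confined to what is unknown.

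In section 6.1.2, add surgery, imaging, injections and hospital admission to the named diary items. Admissions are not among the data listed in section 10.1, so either take them from the diary or add them to the hospital extraction.

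The cost is a few sentences, a few diary items, a small amount of linkage work and a rule against double counting. Extracting admissions, if chosen, is additional work. The change should be made before the economic data are analysed. Any diaries already completed would lack the added items, which is a further reason to rely on the hospital record for these events.

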There has been extensive research on TEI, but these studies generally include patients with chronic sciatica or a mixed population of patients with acute and chronic symptoms. We performed a systematic review on TEI specifically in the acute phase and it occurred that we could find only one article on the efficacy of epidural injections administered to patients with acute sciatica (<8 weeks of symptoms) [6]. This study, conducted by Spijker et al., randomized 63 patients with a duration of symptoms of at least 2 weeks and a maximum of 4 weeks. Patients were divided over an intervention group (receiving TEI with triamcinolone) and a control group (usual care with non-iv medication). It was demonstrated that

functionality and pain relief in the back were more beneficial in the group that received an injection, but that differences were (too) small. However, the analysis of the effect was averaged over all patients in the treatment group. It is known that there is a group of non-responders after TEI, averaging 33% of patients [5]. If the outcome values of all patients are averaged, no effect will be retrieved, while there could be a clear effect for the responders. In the study of Joswig [5] recruiting 63 patients with radicular pain in the leg, 66% of patients responded well to TEI within hours after the injection and in the first 14 days after injection the VAS leg pain remained around 30 mm on a 100 mm scale. In the non-responders the VAS pain was on average 55 mm and persisted on that level for at least 14 days.

Not only was in Spijker's study no distinction made between responders and non-responders, the injection was lacking a painkilling component, like xylocaine. Moreover, the baseline values for VAS leg pain, VAS back pain and Roland Disability score were lower (better) in the control group, and the group of patients evaluated was relatively small. It appears that there is only little literature on TEI in the acute phase of sciatica and therefore additional research is obligatory.

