6.1.2 Secondary study parameters/endpoints

Sciatica is not only characterized by pain in the leg, but also by discomfort in functioning. Therefore the following parameters will also be evaluated.

NRS back pain: The pain intensity in the leg and the back will be measured with a 10-point horizontal Numeric Rating Scale (NRS), ranging from 0 (no pain) to 10 (worst imaginable pain). During each visit the NRS leg pain and NRS back pain will be scored. The patient is not entitled to see the pain scores indicated during previous visit(s). The NRS scores will be measured at baseline and at 1, 2, 4, 10 and 21 weeks after randomization.

Oswestry Disability Index (ODI): The functionality of the patient with a focus on walking and daily activities will be measured with the Oswestry Disability Index that is usually measured for sciatica complaints. The scale ranges from 0 (no disability) to 50 (worst disability possible). During each visit the ODI will be scored. The patient is not entitled to see the scores indicated during previous visit(s). The ODI scores will be measured at baseline and at 1, 2, 4, 10 and 21 weeks after randomization.

EuroQoL (EQ-5D): The EuroQoL (five point EQ-5D) will be used for the cost utility analysis. The tool measures five dimensions: mobility, self-care, daily activities, pain/discomfort, and anxiety/depression. Each dimension consists of one item, while three levels are distinguished (no problems, some problems, many problems). Use of the EuroQoL needs to be registered

(euroqol.org). The EuroQol scores will be measured at baseline and at 2, 10 and 21 weeks after randomization.

Quality of Life VAS (Health state utility VAS): To represent the patients perspective, utility will also be estimated using a VAS for the valuation of the patient's health state (ranging from 0 = as bad as death to 100 = perfect health), measured at baseline and at 2, 10 and 21 weeks after randomization.

Likert perceived recovery patient: To measure the perceived recovery a seven-point Likert scale will be used. The score on this scale varies from 'completely recovered' to 'worse than ever'. The Likert scores will be measured at baseline and at 1, 2, 4, 10 and 21 weeks after randomization.

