6.2 Randomisation, blinding and treatment allocation

Randomisation will take place using block randomisation in a 1:1 allocation ratio in order to obtain equal study groups. When the patient is enrolled, a randomization envelope will be opened to determine patient allocation. Since this is an open-label randomized controlled trial allocation is not concealed.

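### Section 8.2 specifies no baseline-utility adjustment for the QALY and net-benefit comparison, although baseline EQ-5D and VAS are collected

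*Combined protocol and SAP*

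**What the plan says.** The economic evaluation is described in section 8.2. On effects it says "QALYs will be calculated as the area under the utility curve, estimated using the Dutch tariff for the EQ-5D". On the comparison between arms it says "Average costs and patient outcome will be compared according to intention-to-treat, using net-benefit analysis, and using multiple imputation to account for missing data". No regression model or covariate is named for QALYs, costs or net benefit. The one QALY sensitivity analysis changes the valuation and nothing else: "As sensitivity analysis, QALYs will also be calculated using the VAS for quality of life (with power transformation".

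The covariate needed for adjustment exists. Section 6.1.2 says "The EuroQol scores will be measured at baseline and at 2, 10 and 21 weeks after randomization", and gives the same schedule for the quality-of-life VAS. Section 6.2 says "Randomisation will take place using block randomisation in a 1:1 allocation ratio" and mentions no stratification, so balance in baseline utility is left to chance. Elsewhere in section 8.2, EQ-5D itself is analysed as change from baseline to 2 weeks; the QALY, built from the same scores, has no baseline term.

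On the order of events, section 6.3 mentions randomisation before the hospital visit at which baseline questionnaires are completed, while section 10.1 places baseline collection at inclusion. Section 6.2 says the allocation is not concealed.

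**The concern.** A QALY computed as an area under the curve includes the baseline score. It also depends on baseline through later scores, because patients who start with higher utility tend to stay higher. If one arm starts higher by chance, part of that head start is counted as treatment effect. With about 128 evaluable patients and 21 weeks of utility data, the incremental QALY is likely to be small, so a modest imbalance could be a noticeable share of it and would carry into net benefit, multiplied by the willingness-to-pay threshold.

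An unspecified adjustment also leaves the choice of model open until the data have been seen. Cost-effectiveness is a stated secondary objective (section 2), and the results are meant to reach guideline authors (section 10.6).

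**Working it through.** **1. Patients per arm.** Section 4.4 gives a difference of 1.5, SD 2.6, power 90% and significance 5%. The normal formula, taken two-sided, gives n = 2 × (1.960 + 1.282)² × (2.6/1.5)² = 2 × 10.51 × 3.004 = 63.1, so 64 per arm. With 10% loss, 128/0.9 = 142.2. The plan's 64, 128 and 142 reproduce to within rounding. They are used here only to supply n = 64 per arm; the plan gives no figure for the QALY comparison.

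**2. Weight of each visit.** The trapezoid rule on 0, 2, 10 and 21 weeks gives:
- baseline: 2/2 = 1 week
- week 2: 10/2 = 5 weeks
- week 10: (21 − 2)/2 = 9.5 weeks
- week 21: (21 − 10)/2 = 5.5 weeks

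The sum is 21 weeks. Baseline carries 1/21 = 4.8% directly, and the follow-up scores carry 20 weeks. Section 8.2 speaks of an economic evaluation "with a half-year time horizon"; the 21 weeks used here are the span over which EQ-5D is actually measured.

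**3. Shift from a baseline imbalance.** Let D be the baseline difference between arms and b the slope of follow-up utility on baseline utility. Then:
- QALY shift = D × (1 + 20b)/52
- standard error of D = SD × √(2/64)

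The documents give neither SD nor b, so both are assumptions shown over a range. For D equal to one standard error:

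| Assumed SD | SE of D | b = 0.2 | b = 0.3 | b = 0.5 |
|---|---|---|---|---|
| 0.15 | 0.027 | 0.0025 | 0.0036 | 0.0056 |
| 0.20 | 0.035 | 0.0034 | 0.0048 | 0.0075 |
| 0.25 | 0.044 | 0.0042 | 0.0059 | 0.0093 |
| 0.30 | 0.053 | 0.0051 | 0.0071 | 0.0112 |

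The range is about 0.003 to 0.011 QALY. At b = 0 the effect nearly vanishes: D = 0.05 gives 0.05 × 1/52 = 0.001.

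**4. Scale.** A utility gain of 0.10 (assumed) is worth 0.10 × 8/52 = 0.0154 QALY if it lasts 8 weeks, or 0.10 × 21/52 = 0.0404 if it lasts all 21 weeks. The shifts above are 17 to 73% of the first and 6 to 28% of the second.

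**5. Precision.** Assume SD 0.25 at every visit, correlation 0.6 among follow-up scores, and correlation b between baseline and each follow-up score (equal to the slope when the SDs are equal). In squared weeks, the variance factor of the area is 1 + (25 + 90.25 + 30.25) + 2 × 0.6 × (47.5 + 27.5 + 52.25) + 2 × b × 20 = 299.2 + 40b. Adjusting for baseline removes (1 + 20b)². The SE of the QALY difference is 0.25 × √(factor) × √(2/64)/52.

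- b = 0.3: the factor falls from 311.2 to 262.2, and the SE from 0.0150 to 0.0138, a cut of 8%.
- b = 0.5: the factor falls from 319.2 to 198.2, and the SE from 0.0152 to 0.0120, a cut of 21%.

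**The case against.** Several stronger readings are tempting, and the documents do not support them.

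- A reader might infer that the plan has decided on an unadjusted comparison. It has not said so. Net-benefit analysis can be run as a regression with covariates. What can be said is that no adjustment is specified. Multiple imputation does not fill the gap: it handles missing data, even if baseline scores enter the imputation model.
- A reader might infer that the analysis is biased. Under 1:1 randomisation the unadjusted contrast is unbiased over repeated trials, and its standard error already allows for chance imbalance. What remains is conditional bias in the trial actually run, and lost precision.
- A reader might infer that an imbalance carries over in full. Only 4.8% of the area is the baseline score; the rest depends on a slope that the documents do not give. Entry requires leg pain of 6 or more (section 4.2), which could narrow the spread of baseline utility and weaken the slope.
- A reader might infer that an ordinary imbalance could reverse the sign of the result. Even the largest one-SE shift above, 0.011, is below the smaller benchmark of 0.0154. At SD 0.25, cancelling that benchmark takes a two-SE imbalance in the unfavourable direction, with probability about 2 to 3%. It also takes a slope of about 0.40: 2 × 0.0442 × (1 + 20 × 0.40)/52 = 0.0153.
- The introduction does criticise the earlier acute-phase trial because "the baseline values for VAS leg pain, VAS back pain and Roland Disability score were lower (better) in the control group". That shows the authors are aware of the issue, but it concerns pain and disability in 63 patients, not utility, so it is weak support.

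These objections limit the size of the point and how it should be worded. They do not remove it: nowhere do the documents supply the adjustment, and using the collected baseline scores costs nothing.

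**Conclusion.** The point holds as a gap in specification with a free improvement available. Without adjustment, a one-SE chance imbalance would move incremental QALYs by roughly 0.003 to 0.011, given an assumed utility SD of 0.15 to 0.30, a slope of 0.2 to 0.5 and 64 per arm. If the slope is near zero, the matter is negligible. The precision gain of about 8 to 21% in the standard error rests on SD 0.25, slope 0.3 to 0.5 and a follow-up correlation of 0.6. None of these inputs comes from the documents, so confidence is high that the adjustment is unspecified and only moderate about how much it matters.

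The cost-utility analysis is secondary. The primary endpoint, its t-test and the sample size are unaffected.

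**What to change.** In section 8.2, state that incremental QALYs and net benefit will be estimated by regression on treatment arm with baseline EQ-5D utility as covariate, fitted within each imputed dataset and then pooled. For the VAS-based sensitivity analysis, use the baseline VAS instead.

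In sections 6.2 and 6.3, state that baseline EQ-5D and VAS are completed before the allocation envelope is opened. This is an open-label trial and the present text does not fix the order. A baseline score given after the patient knows the allocation may itself be influenced by it, and adjusting for such a score could introduce bias.

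The cost is one sentence in section 8.2 and one on the order of baseline collection. No new data, visits or patients are needed. The change should be made before the data are examined by arm.
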